Ecological Momentary Assessment Measures (EMA; phone based). EMA is currently the most accurate way to measure phenomena in near real-time in natural settings.^{42,44} Thus, EMA methodology will enable the identification of key variables that predict study outcomes with less bias than traditional in-person

Table 2. In-person assessment measures

Demographics/Background
Demographic Information Questionnaire
Homelessness Questionnaire
Arrest History ⁵¹
Health, Mental Health, & Health Behavior
Patient Health Questionnaire ⁵² (depression/anxiety/alcohol)
Mental Health Component from the SF-12 ⁵³
Health Related Quality of Life ⁵⁴
Alcohol and Drug Timeline Follow Back ⁵⁵
88 COVID-19 Vaccine
Common Measures for Adult Well-Being ⁵⁶
Stress/Stressor Measures
Discrimination ⁵⁶
Urban Life Stressors Scale ⁵⁷
Personal Victimization ⁵⁸
Perceived Stress Scale – Short Version ⁵⁹
Negative Affect
Aggression ⁶⁰
Positive and Negative Affect Schedule ⁶¹
Loneliness Scale ⁶²
Interpersonal/Intrapersonal Resources
Interpersonal Support Evaluation List-12 ⁶³
Religious Participation

assessments. At the randomization visit, those assigned to the UCM+SP and SPCM conditions will be trained on how to use the smartphone to complete EMAs and how to use the “Call Study Staff” and “Payment” button/options. Those assigned to the SPCM condition will be trained to use the features of the full smartphone app. All participants who receive smartphones will be prompted by the phone to complete one EMA 30 minutes after waking each day for 6 months beginning the day after the randomization visit. After completion of the EMA, a joke or link to a joke will be presented to the participant via the smartphone. EMA data, collected over a 6-month period, will be used to identify key risk and protective factors that significantly impact substance use, re-arrest (i.e., re-arrest rates tend to peak within 6-12 months of jail discharge⁶⁷), and continued homelessness (homeless episode duration peaks at 180-190 days;^{68,69} see Aim 3).

EMA Assessments. The EMA methodology that will be used in this study is similar to that developed by Shiffman and colleagues^{43,70,71} and was used in our previous studies. EMA items will assess multiple constructs that are hypothesized to be related to the study outcomes (see examples in Table 3). The phone will audibly and visually cue EMAs for 5 minutes, 30 minutes after each participant’s self-reported usual waking time. If the participant does not respond to the EMA prompt, the EMA will be recorded as missed and another prompt will be pushed later that day (this will reduce the likelihood of missed EMAs). EMAs will take approximately 2-4 minutes to complete. All EMAs will be date and time stamped for future analyses. Daily EMA items will ask about current affect and stress. In addition, participants will be asked a number of questions about the prior day that are hypothesized to be related to study outcomes (see Table 3). On Mondays, the daily EMA items and additional items will be assessed. Additional Monday items will cover topics/variables that have less day to-day variability (e.g., arrest; witnessing crimes or violence; emergency room visits; hospitalization; quality of life). Examples of EMA constructs that will be assessed are listed in Table 3 and actual EMA items are included in table

Compensation. Participants will receive compensation for completing each in person visit (i.e., Visits 1 and 2 = \$30; Visits 3-5 = \$50) in the form of gift cards (via Greenphire). Participants who receive study phones will also be compensated based upon the percentage of EMAs completed. Participants who are randomized to receive a smartphone, will have the opportunity to earn additional payment every 15 days for completing daily surveys on the phone. Participants will not receive payment for EMA surveys until they confirm or update the locator information (research staff will attempt to contact participants every 15 days). The level of payment for these daily surveys will depend upon the number of EMA surveys that are completed within each 15-day period. If participants complete at least 13 EMA surveys within a 15-day period, they will receive \$50, if they complete at least 11 EMA surveys within a 15-day period, they will receive \$30, and if they complete at least 7 EMA surveys within a 15-day period, they will receive \$20. Participants will be able to track the number of EMA surveys they have completed by clicking a button on the phone. Payments or completing QDS questionnaires will be issued at scheduled in-person visits only.

Data and Safety Monitoring:

The study poses minimal risk to participants; therefore, the co-Principal investigators (Drs. [name] and [name]) will continuously monitor and report any adverse events. Review of the data and safety monitoring plan (e.g., procedures for screening and consenting participants, computer and phone-based data storage) will occur during the monthly research team meetings. Adverse events are not expected. Although unlikely given our experience, any unanticipated problems (adverse events, protocol deviations, other problems) will be promptly reported to the IRB. The NIH will be informed of any actions taken by the IRB as a result of its continuing review.

Table 3. EMA measures.

Daily Assessments
Positive and Negative Affect ⁶⁶
Sleeping Arrangements
Social Support and Interactions
Perceived Stress & Current Stressors
Discrimination
Prescription Medication Use
Alcohol Consumption
Other Illicit Substance Use
Meal Consumption
Weekly – Monday Assessments
Arrest
Employment
Crime/Violence
Emergency Room Visits
Hospitalization
Quality of Life Items
Pandemic Stress Index (PSI)

Statistics

All randomized participants will be included in the analyses and the trial will end once 462 participants are randomized and complete all study components. Preliminary data analyses, manuscript preparation, and conference presentations will begin in Year 2.

Aim 1. The number of participants ($n = 144$ in each group) was estimated based on the following assumptions: 1) random allocation of participants between 3 conditions; 2) type I error rate set to 0.05; 3) a 30% dropout rate for each condition;²³ 4) targeted minimum power of 0.9, and 5) a conservative increase of 4.5 case management sessions between the UCM and SPCM conditions across the 6-month study period. The estimated increase in in case management sessions is based on Lucht et al.,⁴⁹ which showed that 20% of all phone-based prompts to connect with an alcohol treatment counselor resulted in actual treatment sessions. Mondays, the daily EMA items and additional items will be assessed. Additional Monday items will cover topics/variables that have less day-to-day variability (e.g., arrest; witnessing crimes or violence; emergency room visits; hospitalization; quality of life). Examples of EMA constructs that will be assessed are listed in Table 3 and actual EMA items are included in the Appendix.

	Compensation (Usual Care)	Compensation (Smartphone Groups)
Visit 1 (Today)		
Questionnaire	\$30	\$30
Visit 2 (Within 3 Days)	\$30	\$30
Visit 3 (1-Month Follow-Up)		
Questionnaire	\$50	\$50
Phone Assessments	N/A	Up to \$50 every 15 days for survey completion (\$100)
Visit 4 (3-Month Follow-Up)		
Questionnaire	\$50	\$50
Phone Assessments	N/A	Up to \$50 every 15 days for survey completion (\$200).
Visit 5 (6-Month Follow-Up)		
Questionnaire	\$50	\$50
Phone Assessments	N/A	Up to \$50 every 15 days for survey completion (\$300).
TOTAL:	Up to \$210	Up to \$810

Analyses. Primary analyses for this aim will compare counts of the total number of case and crisis management sessions that occurred between the randomization visit and the 6-month follow-up across the 3 conditions using analysis of covariance (ANCOVA). Covariates may include race/ethnicity, age, sex, lifetime months homeless, type of arrest (e.g., violent vs. non-violent), substance abuse or mental health diagnoses,

and education. The Tukey-Kramer adjustment will be used to examine all pairwise comparisons across conditions. We will also determine if the intervention has similar effects across races, gender, and age**Aim 2**. Based on the available data in criminal justice and homeless populations, we expect a 30% reduction in alcohol and drug use days in SPCM and a 15% reduction in alcohol and drug use days in UCM+SP compared with UCM.^{3,126} Given these expected differences, the proposed sample size of 462 participants (144 per condition) will yield 90% minimum power for comparing the frequency of alcohol and drug use days across conditions. Furthermore, the proposed sample size of 462 participants has 80% minimum power to detect a 24% greater decrease in psychiatric symptoms¹²⁷ in the SPCM group and 10% greater decrease in the UCM+SP group relative to UCM.

Analyses. Multi-level models, also known as mixed models will assess the impact of condition on alcohol and drug use and psychological distress. This method considers the auto correlated nature of this data, and 'unstructured' covariance may be specified to account for the unequal spacing of observations (in-person and EMA data). Covariates for analyses will include baseline characteristics that are known predictors of each outcome, including age, race/ethnicity, employment status, criminal history, and periods of lifetime homelessness. We will also test for interactions between treatment and key demographic variables (e.g., race, ethnicity, gender, and age).

Aim 3. The detectable effects for analyses based on a complete EMA sample size of 201 participants (allowing for 30% study drop-out; see [name] and Rosenheck³ for follow-up rates in a sample of homeless adults with both serious mental illness and substance abuse), 2-sided tests, alpha=.05, and power=.80 are presented in Table 8. Where appropriate, these estimates account for the fact that repeated observations from the same person will be correlated. The most conservative detectable effects for the GLMM EMA analyses will be presented. Thus, calculations are based on an N of 201 individuals completing 80% of 183 assessments during the 6-month EMA study period for a total of 29,426 EMAs across all participants. Since few EMA studies have been conducted in this population, we computed detectable effects using a reasonable range of intraclass correlation coefficient (ICC) values. Detectable effects estimates depend on the variance inflation factor (VIF)¹³⁴ which is based on both the size of the ICC and the average number of observations per person. The VIFs used to calculate the effective sample size are displayed in Table 8. Thus, using the EMA data, we will be able to detect factors that predict reductions in homeless nights by as little as 3.1 percentage points.

Analyses. Logistic Regression of traditional in-person assessments (e.g., substance use, social support, psychological functioning, quality of life; see Table 7 for other key constructs) and summarized EMA data (e.g., affect, stress, discrimination, alcohol and drug use) will be conducted to identify significant demographic, psychosocial, environmental, and behavioral predictors of re-arrest in the 12 months following the randomization visit (binary outcome). Covariates may include treatment group, age, gender, race/ethnicity, education, type of crime, and other variables as appropriate. Change scores (e.g., change in social support from baseline to the 1-month follow-up visit) will also be examined as potential predictors of re-arrest.

Generalized Linear Mixed Model Regression Analyses (GLMM) will be used to examine the longitudinal effect of key risk and protective factors on number of homeless nights (measured repeatedly using a timeline follow-back procedure at in-person follow-up visits). GLMM can handle fixed and random effect model parameters, nested designs, and repeated measures with various correlation structures.^{128,129} GLMM can also handle different variance functions, unbalanced designs where the number of repeated observations varies across individuals, and the situation where assessments within a week are more highly correlated than assessments separated by multiple weeks or months. We will assess the best way to model the correlation of the repeated measures using the methods of Wolfinger¹³⁰ and statistics such as Akaike's and Schwarz's information criteria. Adjustments for multiple comparisons will be made according to Westfall and Young.¹³¹

GLMM will also be used to identify proximal predictors of homeless nights (assessed each day) using EMA data. EMAs generate an enormous amount of data; therefore, we will be able to address multiple within

and between subject questions. For example, we will examine key EMA variables (e.g., negative affect, stress) and parameters (e.g., intercept, slope, quadratic term, volatility) as potential predictors of homeless nights. This invaluable information may be used to detect high-risk situations that may be targeted in future “smart interventions.” EMA data will also allow us to address other important exploratory questions like: 1) what psychosocial changes occur as an individual moves from homelessness into housing, and 2) what effect do events like exposure to discrimination, violence, or hospitalization have on homeless nights.

Mediation. The PROCESS macro for SPSS/SAS (described in Hayes, 2013;¹³² and available online¹³³) will be used to conduct exploratory mediation analyses to identify variables that mediate the relation between condition and homeless nights and re-arrest outcomes. This method uses an ordinary least squares path analytic framework to estimate direct and indirect effects in single and multiple mediation models with bootstrapped confidence intervals. The macro can also be used to evaluate moderated mediation models including those with dichotomous outcomes (e.g., arrest vs. no arrest).

Ethics:

Approval for this study is being sought from the Committee for the Protection of Human Subjects (CPHS) of the University of Texas Health Science Center at Houston. Individuals who were released from the Dallas County Jail or the Dallas City Jail in the past month and present at The Bridge will complete a shelter intake form, be given a Bridge identification badge, and enroll in the Bridge Homeless Recovery program if interested (this is the current standard of care at The Bridge). These individuals will receive information about this completely voluntary study and will be informed that Bridge services are not contingent upon study enrollment. Eligible adults who remain interested the study will be directed by The Bridge Triage/Intake Coordinator (see Bridge Subcontract) to the study research staff for screening. Informed consent will be obtained prior to screening for this study.

Data handling and record keeping:

General Procedures. Each participant will be assigned an identification number that will be utilized in place of names in all electronic and print data files. The sheet containing the links between participant names and identifiers will be kept in locked filing cabinet when not in use and will be destroyed 12 months after data collection has been completed. All print information, including informed consent and screening questionnaires, will be stored in a separate locked filing cabinet in [name] office. All electronic data (with names omitted) will be maintained on the investigator’s computers, and all computers and electronic files will be password protected. Because sensitive data will be collected, a Certificate of Confidentiality has been obtained to ensure that data cannot be subpoenaed and used against participants in court, and this information will be explained to all participants during the informed consent process.

In-person data. Participants will complete questionnaire data on a laptop or tablet computers using the Questionnaire Development System (QDS) program. Participants will wear headphones and the computer will read each question aloud. Participants will be instructed that they may elect to not answer questions that they choose not to answer. When in-person visits are not possible, follow-up visits may occur by phone. QDS does not allow participants to exit without a password. Thus, participants will not have access to other programs or files on the computer. In addition, all questionnaire data is automatically saved and password protected. At the end of each day, participant data will be removed from the laptop/tablet computers and saved into a password protected database. To ensure that research staff are adequately trained in data collection, confidential, and the protection of human subjects, all project staff will complete extensive training focused on each of the following topics: 1) project rationale and objectives; 2) the informed consent process; and 3) general data collection procedures (e.g., computer data collection, privacy). They will also complete all confidentiality, conflict of interest, and HIPAA training programs bi-annually as required by the University of Texas School of Public Health. To maintain the integrity of the data, participants will be required to show identification at each

follow-up visit prior to completing the study assessments.

EMA data. Participant responses to study questions will be encrypted and stored on the study smartphone. Encrypted data will be automatically uploaded to our secure server multiple times each day. The following features are designed to ensure the security of EMA data: 1) the data stored on the smartphone device is in a SQLite database in a sandbox environment, where read/write operations are only available through the programming application (i.e., no file or output is readable to end users); 2) a 10 character password (only known to researchers) is required to authenticate the current user before data can be manually accessed or manually downloaded from the smartphone to the server; 3) the web browser application linking the investigator's computer to the database is on HTTPS protocol (SSL certificate with encryption) which will guarantee the data transfer from web browser to the backend database is well protected; and 4) the backend database is hosted by Microsoft Azure servers and the University of Oklahoma Health Sciences Center in a secure setup. These steps will ensure the security of EMA data.

Arrest data. A list of participant names will be shared with a single Dallas County employee. As stated in the letter of support, the Dallas County Jail ([name], Director of Criminal Justice) will send [name] an encrypted database every 6 months that contains a list of arrested participants, dates of arrest, and charges filed in Dallas County. [name] will use this database to identify study participants who were re-arrested within the 12 months following the date of randomization. [name] will create a new database that includes the participant identification number, date of re-arrest, and class/type of alleged crime. Participant names will not be included in this newly created dataset. This re-arrest data will eventually be merged into the master dataset. Each iteration of the Dallas County Jail dataset will be deleted/destroyed after [name] extracts relevant information. The Dallas City Jail database will be searched to augment arrest data from the Dallas County Jail.

Certificate of Confidentiality. Participants will be asked to answer questions about private information that may have legal consequences if it were disclosed. Therefore, before data collection is initiated, researchers will obtain a Certificate of Confidentiality to protect participants from the mandated release of study data. All participants will be informed that this Certificate has been obtained, and what protections it affords them during the informed consent process. Participant data will not be released to any party outside the research team.

Quality control and assurance:

Drs. [name] and [name] will develop data management and quality assurance procedures for the study data, which will continue through all years of this project. Quality assurance procedures will include a data collection protocol documented in a protocol manual and regular meetings between Drs. [name], [name], [name], and other project staff. The QDS data entry system provides field checks, range checks for continuous variables, valid value checks for categorical variables, checks for legitimate dates and times, and logical consistency. All EMA data and jail provided arrest data will be encrypted and secured on the researcher's password protected computers at the moment of receipt and through all years of the project. Preliminary analyses will be initiated shortly after data collection begins to assess data quality. [name] will be primarily responsible for overseeing data cleaning and data preparation (e.g., combining of EMA, QDS, REDCap and Arrest datasets) for analyses.

Publication Plan

Data analyses, manuscript preparation using preliminary data, and conference presentations will begin in Year

All participants will be mailed a brief summary of the main study findings within 12 months of study completion. References

1. Current statistics on the prevalence and characteristics of people experiencing homelessness in the United States. 2011. (Accessed July 21, 2014, at

[http://homeless.samhsa.gov/ResourceFiles/hrc_factsheet.pdf.\)](http://homeless.samhsa.gov/ResourceFiles/hrc_factsheet.pdf.)

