There is a significant revolving door of incarceration among homeless adults, a population with substantial health disparities. Homeless adults who receive the professional coordination of individualized care (i.e., case management) during the period following their release from jail experience fewer mental health and substance use problems, are more likely to obtain stable housing, and are less likely to be re-incarcerated. The proposed study will use mobile technology to address these barriers and fill gaps in the understanding of the causes of the revolving door of homeless incarceration. Specifically, 462 homeless adults who enroll in a shelter based Homeless Recovery Program after release from county jail will be randomly assigned to one of three treatment groups: 1) usual shelter-based case management (UCM), 2) UCM plus a study provided smartphone (UCM+SP), and 3) UCM with a study provided smartphone that is preloaded with an innovative care management app (SPCM). The SPCM app is an extension of the research team's previous successful work using mobile devices to assess and modify health behaviors in low income and homeless adults. Those assigned to SPCM will receive smartphones that will prompt (twice weekly) connections to shelter based case managers. The app will also offer direct links to care managers (available during normal business hours) and crisis interventionists (available 24 hours a day, 7 days a week), with the touch of a button. It is hypothesized that SPCM will increase utilization of case and crisis management services thereby addressing unmet needs (e.g., obtaining shelter, clothing, counseling, identification) and reducing homelessness and re-arrest. Another key focus of this study is to address gaps in the understanding of mechanisms that drive re-arrest and homelessness by using traditional in-person (i.e., baseline, 1, 3, and 6 months post-baseline) and smartphone based (i.e., daily for 6 months) assessment methods to identify distal and proximal predictors (e.g., affect, thoughts, behaviors, events) of continued homelessness and arrest. This research represents a step toward integrated service connection and healthcare service provision for one of the most undeserved, high need, and understudied populations in the United States. Smartphone apps that increase the use of available healthcare services and identify predictors of key outcomes (e.g., homelessness, re-arrest, medication compliance) could be used to reach hard to reach populations with histories of significant and persistent health disparities (e.g., homeless adults).

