- c. **To identify key factors (alcohol and drug use, social support, psychological distress, quality of life) that predict re-arrest and nights spent homeless using traditional and smart phone-based assessment approaches.** It is hypothesized that key variables that are measured in- person (e.g., alcohol/drug use, perceived social support, psychological distress, quality of life) and via daily phone-based assessments (e.g., affect, stress, discrimination, alcohol/drug use) will have direct effects on re-arrest and number of homeless nights. These key variables are also hypothesized to mediate the relation between treatment condition and number of homeless nights and re-arrest.

Study Design:

This study is a 3-arm randomized controlled trial. Specifically, male and female homeless adults who enroll in a shelter based homeless recovery program following release from either the Dallas County Jail or the Dallas City Jail (N=462) will be randomized to one of three conditions: Usual Case Management (UCM); Usual Care plus Smartphone (UCM+SP); or Usual Care plus Smartphone based Case Management (SPCM). SPCM will be delivered through a modified version of the PI's previously developed smartphone application (i.e., "app") on a study provided smartphone. The app will not provide case management and crisis intervention services directly; rather, it will prompt twice weekly contact with their case manager and provide links to service providers through the touch of a button. Primary study outcomes are service utilization, number of homeless nights, and re-arrest. Another key focus of this study is to address gaps in our understanding of the factors that drive re-arrest and homelessness by using traditional in-person (i.e., baseline, 1, 3, and 6 months post- baseline) and smartphone based (i.e., daily for 6 months) assessment methods to identify distal and proximal predictors of continued homelessness and arrest. Arrest records will be examined to determine if participants are re-arrested within 12 months of study enrollment.

Participants who are randomly assigned to the UCM+SP or SPCM conditions will receive a smartphone at the randomization visit and they will be asked to carry it with them at all times for 6 months (26 weeks). Date, time, location, and duration of SPCM app feature use (e.g., case manager calls) will be recorded by the app for future analysis. See Table 1 for a summary of study conditions.

Study Conditions

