3. **Arrest data.** The Dallas County Jail collects and maintains a dataset that contains demographic characteristics (including homelessness status), and arrest data on all individuals who are arrested in the County. [name] will have access to this dataset for the purposes of this study (see **Director of Criminal Justice Letter of Support**). Specifically, [name] will receive a complete updated and encrypted dataset of all arrested study participants from a Dallas County employee every 6 months. Upon receipt, she will search the dataset for study participants and record whether a participant was arrested or not, the date(s) of arrest, and the class and type of the alleged crime (e.g., violent vs. non-violent, property crime, misdemeanor, felony) in a new study dataset. This arrest data will be used as one of the primary outcome variables for this study. Dallas City Jail records are publicly available online at <https://www.municipalrecordsearch.com/dallastx/Cases>. This database will augment County Jail records and be searched to determine eligibility and arrest.

Study Population:

Consistent with our previous research with this population, we have limited exclusion criteria so that the sample is as broad and representative of the population as possible. Interested individuals (N=462 will be included in the study if they: 1) were released from Dallas County Jail in the past 60 days; 2) plan to reside in the Dallas area for the next year, 3) enroll in The Bridge Homeless Recovery Program, 4) are willing and able to attend the visit, randomization visit, and the 1, 3, and 6-month follow-up visits; 5) score ≥ 4 on the REALM- SF indicating > 6 th grade English literacy level (i.e., a 7th grade reading level is necessary to complete assessments; 12% to 14% of those screened for Projects Advance and Aspire had REALM scores < 7 th gradereading level; < 1 % of Bridge guests are non-English speakers), 6) read aloud from the Informed Consent document to ensure understanding, and 7) score > 24 on the Mini-Mental State Exam indicating no substantialcognitive impairment.

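### Homeless nights and re-arrest are declared primary outcomes, but the plan pre-specifies no confirmatory comparison of the randomized arms for either

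*Combined protocol and SAP*

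**What the plan says.** Study Design lists three primary outcomes: "Primary study outcomes are service utilization, number of homeless nights, and re-arrest". The Arrest data item under Sources of Materials repeats the status of one of them: "This arrest data will be used as one of the primary outcome variables for this study". General Information gives the hypothesis: the app should raise service use, "thereby addressing unmet needs (e.g., obtaining shelter, clothing, counseling, identification) and reducing homelessness and re-arrest".

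The Statistics section is organised by aim:

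- **Aim 1.** "Primary analyses for this aim will compare counts of the total number of case and crisis management sessions", by ANCOVA across the three conditions, with Tukey-Kramer for the pairwise comparisons.
- **Aim 2.** Mixed models "will assess the impact of condition on alcohol and drug use and psychological distress".
- **Aim 3, re-arrest.** A logistic regression searches for predictors of re-arrest in the 12 months after randomization, using in-person measures and summarized EMA data. On adjustment: "Covariates may include treatment group, age, gender, race/ethnicity, education, type of crime, and other variables as appropriate". Also: "Change scores (e.g., change in social support from baseline to the 1-month follow-up visit) will also be examined as potential predictors of re-arrest".
- **Aim 3, homeless nights.** A GLMM relates risk and protective factors to homeless nights. No condition term is named.
- **Mediation.** Models linking condition to homeless nights and re-arrest, labelled exploratory.

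The only sizing that mentions either outcome is in Aim 3, for 201 people: "we will be able to detect factors that predict reductions in homeless nights by as little as 3.1 percentage points".

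**The concern.** Both outcomes are collected in all three arms, and the trial's rationale is that the app will reduce them. Yet the plan, followed exactly, produces no confirmatory estimate of the effect of assignment on either. A treatment coefficient from the re-arrest model would not serve. Condition may be left out of that model. If it is included, it can sit beside EMA summaries and change scores measured after randomization, so its coefficient is not the total effect of assignment.

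A claim that the app does or does not reduce homelessness or re-arrest would then rest on an exploratory mediation output, or on a treatment term, covariate set and threshold settled after data are available. The plan begins preliminary analyses in Year 2, while the study is running, so that risk is real. If each of the three primaries were tested at 0.05, the family-wise error would be 1 - 0.95^3 = 14.3% were they independent, and no rule across them is stated.

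**Working it through.** **1. Outcomes against planned arm comparisons**

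| Outcome | Called primary (Study Design) | Pre-specified arm comparison | Between-arm power stated |
|---|---|---|---|
| Service utilization | Yes | Yes (Aim 1, ANCOVA) | Yes |
| Homeless nights | Yes | No | No |
| Re-arrest | Yes | No (condition optional) | No |
| Substance use, distress | No | Yes (Aim 2, mixed models) | Yes |

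**2. The plan's own Aim 3 figure**

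- EMAs: 201 x 183 x 0.80 = 29,426.4. The plan gives 29,426, so it reproduces.
- People: 2 arms x 144 x (1 - 0.30) = 201.6. This matches 201.
- Only the two smartphone arms supply EMA data, so this sample contains no usual-care participants and cannot support a comparison with usual care. The 3.1-point effect concerns predictors. It cannot be re-derived, because the table of ICC and variance inflation values is not in the text.

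**3. Illustration: re-arrest**

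Inputs: two-sided 0.05 and 80% power (as in Aim 3); 144 per arm as stated, or 462/3 = 154; jail records on everyone randomized. The usual-care rate is assumed to be 50%, and then 60%. The documents say only that more than half of adults released from Texas county jails are re-arrested within a year.

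With p1 the usual-care rate, p2 the comparison rate and p their mean, solve

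n = [z_a sqrt(2p(1-p)) + 0.842 sqrt(p1(1-p1) + p2(1-p2))]^2 / (p1-p2)^2

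with z_a = 1.960 unadjusted. For Tukey with three groups, q = 3.314, so z_a = 3.314/sqrt(2) = 2.344 (per-pair alpha 0.0191). Check at n = 154, p1 = 0.50, p2 = 0.343: (1.960 x 0.698 + 0.842 x 0.689)^2 / 0.157^2 = 154 to rounding.

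| Usual-care rate | n per arm | Detectable drop, unadjusted | Detectable drop, Tukey |
|---|---|---|---|
| 50% | 154 | 15.7 points | 17.8 points |
| 50% | 144 | 16.2 points | 18.4 points |
| 60% | 154 | 15.9 points | 18.1 points |
| 60% | 144 | 16.4 points | 18.7 points |

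The unpooled variance lowers these by 0.1 to 0.3 points.

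Power for 50% against 40% at n = 154: the null standard error is sqrt(2 x 0.45 x 0.55/154) = 0.0567 and the alternative is sqrt((0.25 + 0.24)/154) = 0.0564. Then (0.10 - 1.960 x 0.0567)/0.0564 = -0.197, which gives power 0.42 (0.43 unpooled). At 144 it is 0.40. With Tukey it is 0.28 (154) and 0.26 (144).

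**4. Illustration: homeless nights**

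No SD is given, so the scale is SD units. After 30% dropout, n = 0.7 x 154 = 107.8 or 0.7 x 144 = 100.8 per arm.

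- One visit, unadjusted: (1.960 + 0.842) x sqrt(2/n) = 0.38 or 0.39 SD.
- One visit, Tukey: (2.344 + 0.842) x sqrt(2/n) = 0.43 or 0.45 SD.
- Averaged over three visits, multiply by sqrt((1 + 2r)/3), where r is the within-person correlation. With r assumed between 0.3 and 0.7, this gives about 0.28-0.35 SD unadjusted and 0.32-0.40 SD with Tukey.

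**The case against.** The best defence is that the Statistics section follows the aims. Only Aims 1 and 2 set out to compare conditions. Aim 3 sets out to find predictors, so homeless nights and re-arrest are simply its dependent variables. The plan is also not silent on condition: Objectives states a mediation hypothesis linking it to both outcomes, the model families (logistic, GLMM) are fixed, and Statistics opens by saying that every randomized participant will be analysed.

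Some of this stands. The analysis population and model families are given, and arm does enter some analyses. What is missing is narrower: a mandatory treatment contrast, its covariates and its threshold. An analysis-set sentence does not supply a contrast, and the mediation hypothesis is tested only in work labelled exploratory. Reading Aim 3 as prediction alone conflicts with the primary label in Study Design and with the expectation in General Information that the app reduces both outcomes.

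Two further points are fair. The scope of the Westfall and Young adjustment is not stated. It sits in the homeless-nights GLMM paragraph and is not tied to the three primaries, so it cannot be taken as a rule across them. And the single-visit SD figures overstate the detectable difference for an effect averaged over visits, which is why both are shown.

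**Conclusion.** The concern holds. Two of the three declared primary outcomes have no pre-specified confirmatory comparison between randomized arms, no between-arm power and no multiplicity rule. This rests on the text alone and must be fixed before the trial can support a claim about homelessness or re-arrest. Relabelling the two outcomes as non-primary would remove the contradiction in Study Design, but would still leave the hypothesis in General Information without a planned test.

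The power figures are illustrations of what an added comparison could show, not measures of the defect. For usual-care re-arrest rates of 50-60%, the detectable drop is 15.6-16.4 points unadjusted and 17.6-18.7 with Tukey, over both sample sizes and both variance forms. Power for a 10-point drop from 50% is 40-43%, or 26-28% with Tukey. For homeless nights the range is 0.28-0.45 SD, depending on adjustment, number of visits and assumed correlation.

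**What to change.** Add to Aim 3 one intention-to-treat comparison of the three conditions per outcome, with condition as a mandatory factor and baseline covariates only (for example the Aim 1 list).

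1. **Re-arrest within 12 months of randomization.** Logistic regression on all randomized participants, from jail records, noting that these cover only the City of Dallas and Dallas County. Align the start of the window: the protocol summary uses the baseline visit and Study Design uses enrollment, while Study Procedures, Aim 3 and the data-handling section use randomization.
2. **Homeless nights.** GLMM on the timeline follow-back data at 1, 3 and 6 months, with condition and time. State the distribution, the denominator of nights for each unequal interval, and whether the target is the average over follow-up or the 6-month value.
3. **Multiplicity.** Use Tukey-Kramer within each outcome, as in Aim 1. Then either state a rule across the three primaries, or name service utilization the single primary and the other two key secondary. Make Study Design and the Arrest data item agree with that choice.
4. **Power.** State the between-arm detectable difference for each outcome.
5. **Predictor and mediation models.** Keep them as secondary.

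The cost is plan wording and two models on data already collected in every arm. The price is a somewhat stricter threshold per outcome and an open statement that power for a moderate effect on re-arrest is limited.
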